5.6 Safety Analyses

5.6.1 Extent of Exposure

Any analysis related to the exposure will be based the SS.

The number and percentage of participants with cumulative IMP duration (e.g. any duration, ≥ 1 week, ≥ 2 weeks, ≥ 3 weeks,, etc.) will be presented by IMP.

IMP duration = Date of Last Dose – Date of First Dose +1

The duration of exposure to each treatment will be summarized by IMP:

Duration of exposure in years (or Participant Exposure Years (PEY)) = $[(\min(\text{Date of Last Dose} + 40 \text{ days, Last Visit}) - \text{Date of First Dose} + 1)] / 365.25$

Thus, exposure will be adjusted for the 5 half-lives of active treatment which is 40 days.

Duration of exposure (100 participant years) = PEY / 100.

Summaries on the treatment exposure and time at risk in subject years will be given.

Participants which are exposed to both treatments will be presented in either study treatments using the corresponding start and stop treatment date.

The number of doses missed (from the eCRF Study drug administration page after Day 1) will be summarized overall and by IMP.

5.6.2 Adverse Events

Adverse events will be captured from the time of informed consent signature (only the SAEs) or from the time of first administration (Treatment Emergent Adverse Events) and will be reported if occurred during scheduled or unscheduled visits. As Treatment Emergent AE (TEAE) is defined as an AE starting on or after the time of first administration of study drug or an AE that increases in severity after treatment start, if the event was present at the time of the treatment initiation. Reporting of TEAEs refer to the period until the administration of the last study dose plus 40 days (or last visit depending which occurs first).

AEs will be classified according to the Common Terminology Criteria for Adverse Events (CTCAE) Version 5.0 for severity. For any AE where it is not possible to provide a CTCAE grading, the event will be assessed using a standard intensity classification (mild, moderate and severe). For the purpose of the tabulations all CTCAE severity classifications will be mapped to a mild/moderate/severe grade as described below:

- Grade 1 - Mild
- Grade 2 - Moderate
- Grade 3, 4, 5 - Severe

These will be tabulated together with the AEs that were not classified according to CTCAE criteria i.e., all Grade 1 AEs as per CTCAE criteria will be included in the ‘mild’ category together with those AEs classified as mild as per the ‘standard’ intensity classification.

If a particular AE severity is missing, then this will be listed as missing and treated as missing in summaries. If a participant has experienced more than one TEAE within the same PT, then the AE with the greatest severity will be presented. If a participant reported more than one AE within the same (System Organ Class) SOC then the participant will be counted only once with the greatest severity at the SOC where applicable.

Where dates are missing or partially missing, AEs will be assumed to be treatment-emergent unless evidence exists that does not allow the AE to be treatment-emergent. Handling of missing dates for classification of AEs as TEAEs is described in Section 5.1.1.8.

TEAE summaries will be performed in SS and repeated in SS_{NOCOVID-19} if at least 15% of the participants have at least one AE as ‘Confirmed COVID-19’.

Summaries may also be repeated in SS among participants with at least one TEAT based on the COVID-19 period defined as:

- Before the pandemic: a TEAE will be assigned to this period if the start date of the event is on or after the date of the first administration of study drug on Day 1 but before the cut-off date of 11th MAR 2020.
- During/after the pandemic: a TEAE will be assigned to the during/after the pandemic Period if the start date of the event is on or after the date of the first administration of study drug on Day 1 but after the cut-off date of 11th MAR 2020.

A TEAE will be counted as related to study drug if the response to the question “Relationship to Study Medication” is “Related”. Severe TEAEs are those with CTCAE Grade 3 or above, or those without a CTCAE grading classified as ‘severe’ by the Investigator. If a participant reports the same event with different relationship assessments, then participant will be counted under both related and not related categories.

Adverse events will be presented as “number of participants (percentage of participants) [number of events]”. In this style of output, “[number of events]” will include all cases of an AE including repeat occurrences in individual participants, while “number of participants” will count each participant only once.

TEAE Summaries will be reported separately within the Main Portion and within the Main and Extension Portion of the study and presented by primary system organ class (PSOC) and preferred term (PT) within each IMP. PSOCs will be sorted alphabetically. PTs will be sorted by decreasing frequency of Zilucoplan within each PSOC; ties will be sorted alphabetically within Zilucoplan. TEAEs will be mapped to a study portion based on the onset date.

The following summaries will be produced:

- TEAE overview table in SS and SS_{NOCOVID-19}, displaying participants with at least one TEAE, with at least one TEAE before/after 11th March 2020, with at least one serious TEAE, with at least one TEAE resulting to permanent withdrawal from study medication, with at least one drug-related TEAE and with at least one TEAE leading to death
- TEAEs by PSOC and PT, in SS
- TEAEs by PSOC and PT by COVID-19 period, in SS
- Serious TEAEs by PSOC and PT in SS
- Serious TEAEs by PSOC and PT for each COVID-19 period, in SS
- TEAEs by PSOC, PT and maximum CTCAE V5.0 Grade, in SS
- TEAEs by PSOC, PT and maximum relationship, in SS
- Serious TEAEs by PSOC, PT and maximum relationship, in SS
- Fatal TEAEs by PSOC, PT and maximum relationship, in SS
- Non-Serious TEAEs by PSOC and PT of at least 5% within any IMP (Main Portion) or active treatment (Extension Portion), in SS
- TEAEs by PSOC and PT leading to drug discontinuation, in SS
- TEAEs by PSOC and PT leading to death, in SS

Of note, the following are not considered to be AEs despite requiring hospitalization:

- Pre-existing conditions that, in the opinion of the investigator, did not worsen or progress during study participation
- Routinely scheduled procedures or treatments
- Elective procedures that were scheduled prior to study participation (i.e., signing of the ICF)

Safety tables for the combined Main and Extension Portion of the study, will display the Treatment Emergent Adverse Event Incidence Rate (AEIR) per 100 patient-years of Zilucoplan treatment (thus no placebo arm to be summarized due to limited exposure time as compared to active). Tables will include the PEY per 100 patient years (as defined in Section 5.6.1), number and percentage of participants with a particular TEAE, the exposure adjusted incidence rate (EAIR) followed by 95%CI and the exposure adjusted event rate (EAER):

- EAIR for TEAEs by PSOC and PT, in SS
- EAIR for serious TEAEs by PSOC and PT, in SS

The EAIR is defined as the number of study participants with a specific new TEAE divided by the duration of exposure of all participants (scaled to 100 participant years). The time at risk for a study participant is censored at the date of this event. If a study participant has no events, the total time at risk (i.e. exposure) is used.

Exact Poisson 95% CIs for EAIR are calculated using the relationship between the Poisson and the Chi-square distribution (Ulm, 1990; Fay and Feuer, 1997):

$$\text{Lower Confidence Limit} = x_{2n,\alpha/2}^2/2$$

$$\text{Upper Confidence Limit} = x_{2n(n+1),1-\alpha/2}^2/2$$

where n stands for the number of participants with a specific TEAE for the incidence rate of interest and is the basis for the number of the degrees of freedom for the chi-square quantile for the upper tail probability χ^2 .

The EAER is defined as the total number of TEAEs including repeat occurrences in individual study participants divided by the total time at risk scaled to 100 patient-years. No confidence interval will be computed for the EAER.

Individual data listing of all AEs (TEAEs and non TEAEs) will be created and displayed by IMP based on the ES. Also, by participant listings for all the TEAEs leading to permanent withdrawal of study drug, for all the TEAEs related to study drug and for all the TEAEs leading to death will be presented by IMP. In each listing, a COVID-19 flag will be present indicating the time frame of the event relevant to the COVID-19 period. A separate data listing for participants with confirmed COVID-19 will be produced.

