11.4.1.1 ADVERSE EVENTS

Pre-existing conditions that are detected prior to administration of the first dose of study drug will be recorded as part of the medical history. For all subjects, the AE reporting period will start with the first administration of study drug on Day 1 (for SAE reporting period, see Section 11.4.1.2) and will end 40 days following the last dose of study drug (i.e., the End of Main Visit, Day 57 Visit, or Final Extension Visit), after which no new non-serious AEs are to be reported. The subjects will be monitored throughout the study for any AEs, including clinically significant findings at vital signs measurements, spontaneous reports by study subjects, and observations by the study personnel.

When possible, ongoing AEs assessed as related to the study drug will be followed until resolved or stabilized. Subjects visit the clinic 40 days after their last dose to gather information on ongoing AEs and report any new SAEs since the last study visit (see Section 11.4.1.2 for SAE reporting instructions).

All AEs will be recorded in the eCRF. The investigator will assess and record any AE in detail including the date and time of onset, event diagnosis (if known) or sign/symptom, severity, time course (end date or ongoing), relationship of the AE to study drug, and action(s) taken. All AEs should be reported separately (i.e., 1 record per event).

Reporting of AEs is event-based (i.e., an ongoing event will not be closed until resolved or at the end of study). For the AE description, a diagnosis is preferred over symptoms. If no diagnosis can be made, each symptom will be reported as a separate AE.

Abbreviations should be avoided. Descriptive words should be used for ongoing conditions as applicable (e.g., [REDACTED]).

AEs will be coded using Medical Dictionary for Regulatory Activities (MedDRA; Version 20.0 or higher) after the eCRFs have been monitored and signed by the investigator.

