11.4.1.2 SERIOUS ADVERSE EVENTS

Any SAE experienced by the subject from signing the ICF through to 40 days after the last dose of study drug, regardless of severity or causality, must be recorded on the eCRF and SAE forms. Subjects visit the clinic 40 days after their last dose to gather information on ongoing AEs and report any new SAEs since the last study visit.

The study site must formally notify the Sponsor (or delegate) of the SAE within 24 hours from the time the study site becomes aware of the SAE. A formal notification must be submitted to the Sponsor regardless of the following:

- Severity
- Causality
- Whether or not the subject received study treatment or underwent study related procedures

The IRB/IEC will be notified as required by local regulations. The investigator will be responsible for submitting the required safety information to the appropriate IRB/IEC, including any safety reports received from the Sponsor as well as any SAEs occurring at his/her site.

The Sponsor, or designee, will prepare any required safety reports for Competent Regulatory Authorities and all active investigators. These reports will be provided as addenda to the IB, and the investigator will place these with the IB. All Competent Regulatory Authorities will be informed as per applicable legislation.

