5.1.1.2.2 Study periods

- **Screening Period** is defined as any time prior to the date/time of first dose of study drug and after the date/time of the ICF signature. Screening period starts at maximum 28 days prior to the randomization day.
- **Treatment Period** is defined as the period on or after the date/time of the first dose of study drug and ends at the date/time of Week 8 visit or at the date/time the participant has performed the End of Study Visit prior to Week 8. If a participant does not have a Week 8 visit or End of Study Visit, then either the date of the last scheduled or unscheduled visit during the Main Portion or the date of the last known dose of study drug during the Main Portion, whichever is later, will define the end date of Blinded Period.
- **Follow-up Period** starts one day after the Week 8 visit and ends after the final assessments on the safety Follow-up visit (40 days later). For participants who permanently discontinue the study during the treatment period, the follow-up period starts the next day and ends 40 days later after the final safety assessments. Participants with assessments after the blinded period

are considered to have started the Follow-up Period provided, they have not entered the Extension Portion of the study.

- **Extension Period** starts one day after the end of Treatment Period and lasts until the day of the final extension visit.
- **Extension Follow-up Period** starts one day after the end of the final extension visit and ends at the day when final assessments are performed on the safety Follow-up visit (40 days later).

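### SAP 5.6.2 stops counting TEAEs at the last visit when that comes before last dose + 40 days, so an event starting after a participant's last recorded visit can drop out of the primary safety tables

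*SAP*

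**What the plan says.** **SAP.** Section 5.6.2 defines a TEAE by onset or worsening after the first dose. The next sentence sets the reporting period, which runs "until the administration of the last study dose plus 40 days (or last visit depending which occurs first". Just before that, the section says AEs "will be reported if occurred during scheduled or unscheduled visits". Last visit is not defined for this purpose. The person-years formula in 5.6.1 uses the same minimum, although that section gives the reason for the 40 days: "Thus, exposure will be adjusted for the 5 half-lives of active treatment which is 40 days". Section 6.3 declares no changes from protocol amendment 2.

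**Protocol.** Section 11.4.1.2 requires recording of "Any SAE experienced by the subject from signing the ICF through to 40 days after the last dose of study drug". The TEAE definition in 12.2.4.1 has no end date and no visit limit. Section 11.4.1.1 says the AE reporting period "will end 40 days following the last dose of study drug", but the same sentence goes on to gloss that date, in brackets, as the End of Main, Day 57 or Final Extension Visit, and closes non-serious reporting there. The SAE window is therefore clear and the non-serious window is not.

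**Outputs.** TEAE incidence is the primary safety endpoint. The SAP 5.6.2 overview counts participants "with at least one TEAE leading to death". The serious, fatal and exposure-adjusted incidence rate (EAIR) tables, and the events of interest in 5.6.3, are also restricted to TEAEs.

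**The concern.** A last-visit limit does little harm to laboratory, vital-sign or ECG data, because those exist only where there is a visit. Adverse events also begin between visits, and here dosing continues daily at home between visits. If an event starts after the last attended visit and prevents any further visit, the limit falls before the event.

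The loss is not random. It falls on events severe or rapid enough that no later visit takes place. SAP 5.6.3 counts Neisseria infections only as TEAEs and prints a zero line where none is counted, whereas protocol 12.2.4.1.1 plans that summary on AEs. A rapidly fatal infection between visits could therefore be collected as an SAE and still be tabulated as zero.

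**Working it through.** The plan states no figure to reproduce. The check applies its date rule to example participants.

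**Inputs.** Main Portion visits fall on Days 1, 8, 15, 29 and 57 (schedules in both documents). Day E1 is Day 57, so E117 is Day 57 + 116 = Day 173. The post-dose period is 40 days. The participant dates below are assumptions.

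**Formulas.** SAP cut-off = min(last dose + 40, last visit). Protocol SAE limit = last dose + 40. On-dose days outside = last dose − cut-off, if positive.

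| Case | Last visit | Last dose | Last dose + 40 | SAP cut-off | Days outside |
|---|---|---|---|---|---|
| A: fatal onset Day 50, still dosing | 29 | 50 | 90 | 29 | 21 on-dose |
| B: doses to Day 56, then lost | 29 | 56 | 96 | 29 | 27 on-dose + 40 post-dose |
| C: completes Day 57, no Extension, no Safety Follow-up Visit | 57 | 57 | 97 | 57 | 40 post-dose |
| D: Extension, fatal onset Day 202, still dosing | 173 | 202 | 242 | 173 | 29 on-dose |
| E: Safety Follow-up Visit on Day 97 | 97 | 57 | 97 | 97 | none |
| F: Safety Follow-up Visit 3 days early | 94 | 57 | 97 | 94 | 3 post-dose |

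The fatal events in A and D lie after the cut-off, so they are not reported as TEAEs.

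**Room for this to happen.** The longest Main Portion gap is 57 − 29 = 28 days, or (57 + 7) − (29 − 2) = 37 with visit windows. From E87 to E117 the gap is 30 days, or 30 + 14 = 44 with windows. Of 57 nominal Main Portion dosing days, 57 − 5 = 52 are not visit days.

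**Exposure.** Person-years under 5.6.1 in case A are 29/365.25 = 0.079. Counted to death they are 50/365.25 = 0.137. In case D they are 173/365.25 = 0.474 against 202/365.25 = 0.553.

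**Conditional illustration.** Suppose a fatal event occurs, onset is uniform over the 56 days between Day 1 and Day 57, and there are no unscheduled visits. For a delay L from onset to death, the share with no visit in between is the sum of max(gap − L, 0) over the gaps 7, 7, 14 and 28, divided by 56:

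- L = 3: (4 + 4 + 11 + 25)/56 = 44/56 = 79%
- L = 7: (0 + 0 + 7 + 21)/56 = 28/56 = 50%
- L = 14: 14/56 = 25%

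With 30-day gaps the shares are 27/30 = 90%, 23/30 = 77% and 16/30 = 53%. These describe hypothetical deaths and do not forecast losses in this trial.

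**The case against.** The strongest reply is that the pattern is uncommon and the events do not disappear. Much of this stands.

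- **Only onset after the last visit matters.** SAP 5.6.2 assigns TEAEs by onset date. A reader might infer that every death after the final visit is lost. That is not so: a death from an event that began on or before that visit still counts.
- **Other outputs keep some events.** A reader might infer that an excluded death survives only in a listing. SAP 5.2 also plans a table by treatment, for each portion, of discontinuations due to AEs, including fatal ones. Deaths must also be reported as SAEs (protocol 11.4.1.3).
- **Follow-up removes the problem.** Anyone attending the Safety Follow-up Visit on time loses nothing, and an unscheduled visit on or after onset keeps the event in. If remote contacts count as visits, fewer events are lost, but the SAP does not say they do.
- **The SAP does not flatly contradict itself.** Section 5.1.1.2.2 has a rule for a missing final visit that compares the last visit with the last dose: "the date of the last known dose of study drug during the Main Portion, whichever is later, will define the end date of Blinded Period". It is tempting to set this against 5.6.2. But it is a fallback for ending a different period, so it is a tension and not two definitions of one quantity.
- **Exposure is not simply misreported.** SAP 5.6.1 also tabulates treatment duration as last dose − first dose + 1, which gives 50 days in case A. The person-years limit matches the TEAE limit, so the rates are internally consistent as written.
- **The protocol is not free of visit language.** The bracket in 11.4.1.1 leaves the conflict unproven for non-serious AEs.

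None of this puts the event back in the TEAE tables. The SAP default that unclear dates count as treatment-emergent does not help when onset is known. The protocol leaves analysis detail to the SAP, but a limit narrower than the protocol's SAE window and TEAE definition sits badly with a statement of no changes.

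**Conclusion.** The rule is wrong as written and should be fixed. Read literally, it leaves out of the TEAE, serious TEAE, fatal TEAE, event-of-interest and EAIR tables any AE with known onset after the last recorded visit but within 40 days of the last dose. That includes onset while still dosing, and onset after an End of Main or Day 57 visit when the Safety Follow-up Visit does not take place. The conflict with the protocol is firm for SAEs and for the TEAE definition.

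The documents give no death rate or missed-visit rate, so the number of events affected cannot be estimated. It may be zero. If one death were excluded, that would be 1/12 = 8.3% of a planned arm. The direction is clear: the exclusion favours dropping rapidly severe or fatal events from the primary safety endpoint. Because listings and the 5.2 table keep such events visible and on-time follow-up removes the loss, this is a should-fix and not a must-fix.

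**What to change.** **SAP 5.6.2.** Count as TEAEs all AEs with onset or worsening from the first dose through last dose + 40 days, whether or not a visit follows. Delete the bracketed last-visit limit for AEs and keep assignment to study portion by onset date. State the window in full and do not refer to protocol 11.4.1.1, whose visit bracket is ambiguous and should be reconciled with its 40-day wording.

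**SAP 5.6.1.** End time at risk at the earliest of:

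- last dose + 40 days;
- death;
- last contact, but never before the last dose;
- for placebo exposure, the first zilucoplan dose in the Extension.

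The last term is needed because placebo exposure extended by 40 days would otherwise overlap zilucoplan exposure in participants who switch. Change 5.6.1 together with 5.6.2, so that the numerator and denominator of the EAIR and the exposure-adjusted event rate (EAER) still cover the same time. The limit can stay for laboratory, vital-sign and ECG summaries.

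**Cost.** One sentence and one formula term. SAEs are already collected over this window. A last-contact date is needed for participants lost to follow-up; SAP 5.1.1.8.3 already uses one.

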5 STATISTICAL ANALYSES

5.1 General Considerations

- Descriptive statistics for continuous endpoints will include number of participants with available measurements (n), mean, standard deviation (SD), median, 25% and 75% percentiles, minimum and maximum. Confidence Intervals (CIs) will be provided where appropriate. In general, all study endpoints will be summarized descriptively by IMP and overall (if applicable).
- Frequencies and percentages will be presented by IMP for categorical and ordinal variables. Unless otherwise noted, the denominator for percentages will be based on the number of participants included in the respective analysis set.

Participants with missing data can generally be accounted for using the following approaches:

- For summaries of demographics and baseline characteristics: summarize percentages based on all participants in the analysis set and include a “Missing” category (corresponding to participants with missing data for the variable being summarized) as the last row in the list of categories being summarized. Percentages are associated with the missing row so that percentages sum to 100.
- For summaries of efficacy and safety variables, unless otherwise specified: summarize percentages based only on those participants with observed data for the variable being summarized. As the denominator may be different from the number of participants in the

analysis set being considered, the denominator should be displayed in the table. The general format for displaying this will be “n/Nsub (%).”

All percentages will be displayed with one decimal place. No percentage will be displayed for zero counts and no decimals will be presented when the percentage is 100%. If there are no missing data for a variable, then the missing row can be removed for that variable in the shell. If there are no observations in any specific eCRF-specified category, then retain that row and present 0's across the table. E.g., if there are no 'American Indian/Alaskan native' participants in the study but this was one of the Racial Group categories in the eCRF, then retain the row and populate it with 0 values.

Decimal places for descriptive statistics will always apply the following rules:

- “n” will be an integer;
- Mean, SD, and percentiles will use one additional decimal place compared to the original data reported;
- CV [%] will be presented with one decimal place;

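### The adverse event tables split at 11 March 2020 have no period-specific at-risk denominator, and that date itself belongs to neither period

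*SAP*

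**What the plan says.** - **Periods.** SAP 5.6.2 assigns each TEAE by its onset. The first period takes onsets from first dose "but before the cut-off date of 11th MAR 2020"; the second takes onsets after that date.
- **Required tables.** The list of summaries in the same section includes "TEAEs by PSOC and PT by COVID-19 period, in SS" and "Serious TEAEs by PSOC and PT for each COVID-19 period, in SS". The overview table also counts participants with a TEAE before or after 11 March 2020. Results are shown as participants, percentage and number of events.
- **Analysis set.** SAP 4 defines the Safety Set as everyone dosed at least once in the Main Portion, with no calendar limit.
- **Default denominator.** SAP 5.1: "Unless otherwise noted, the denominator for percentages will be based on the number of participants included in the respective analysis set". For efficacy and safety variables it adds a second rule: "summarize percentages based only on those participants with observed data for the variable being summarized", with the denominator displayed.
- **A further base.** The sentence that introduces the period split in SAP 5.6.2 reads "Summaries may also be repeated in SS among participants with at least one TEAT based on the COVID-19 period defined as". The abbreviation is presumably a slip for TEAE.
- **Enrolment on both sides of the date.** SAP 5.1 and 6.1.3 split demographics and medical history by enrolment date around the pandemic, so the plan expects participants on either side. No counts are given.

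**The concern.** The calendar split is applied to the events and not to the people. Someone first dosed after 11 March 2020 could not have had a TEAE before it, yet on the default rule sits in the denominator of the earlier period. Someone whose TEAE window (to last dose plus 40 days, or last visit if sooner) closed before the cut-off sits in the denominator of the later period on the same terms.

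SAP 5.1.1.8.2 lists summaries by pandemic period among its means of assessing the impact of COVID-19 on the study. A before/during contrast whose denominators ignore who was at risk mixes the event rate with the enrolment calendar. Separately, the two period definitions leave out the cut-off day, so an event starting then would drop out of both.

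**Working it through.** The plan states no figure on this point, so there is nothing to reproduce. The check is what each stated base does to a period percentage.

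**Inputs**
- N = 12 per arm: planned size, SAP 1.2.
- k = participants per arm first dosed before 11 March 2020: not in the documents; assumed range 3 to 12.
- x = participants per arm with a TEAE before the cut-off: assumed to be one third of k.

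**Default base, earlier period**

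Reported percentage = x/N. At-risk percentage = x/k. Their ratio is (x/N)/(x/k) = k/N, so the relative understatement is 1 − k/N, whatever x is.

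| k of 12 | x | Reported x/12 | At-risk x/k | Ratio k/12 | Relative understatement |
|---|---|---|---|---|---|
| 3 | 1 | 8.3% | 33.3% | 0.25 | 75% |
| 6 | 2 | 16.7% | 33.3% | 0.50 | 50% |
| 9 | 3 | 25.0% | 33.3% | 0.75 | 25% |
| 12 | 4 | 33.3% | 33.3% | 1.00 | 0% |

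**Default base, later period**

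The same algebra applies. If j of 12 have at least one day at risk from the cut-off onward, the reported percentage is the at-risk percentage times j/12. Once 11 March is assigned to a period, every participant has time on at least one side, so k + j is at least 12. Both ratios equal 1 only if every participant's window spans the date.

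**Optional base: participants with at least one TEAE**

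Take k = 6, with 4 participants having any TEAE in the earlier period and 2 having a given preferred term (all assumed).
- Safety Set: 2/12 = 16.7%.
- At risk: 2/6 = 33.3%.
- At least one TEAE in that period: 2/4 = 50.0%.

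On this reading the percentage is at or above the at-risk value. The sentence does not say that the qualifying TEAE must fall in the period. If a TEAE at any time qualifies, the base m lies between 4 and 12 and 2/m runs from 50.0% down to 16.7%, on either side of 33.3%.

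**Observed-data rule**

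SAP 5.1 does not say whether a participant not yet dosed, or already out of follow-up, counts as unobserved for a calendar period. The rule therefore supplies no at-risk definition.

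**Time at risk**

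TEAEs are reported for the Main Portion and for Main plus Extension. Outside France the Extension has no fixed end (Protocol 7.2), so in the combined tables time after a fixed date keeps accruing while time before it cannot. SAP 5.6.2 plans exposure-adjusted rates for the combined portions on zilucoplan, but not by period.

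**The case against.** **The base is not fixed.** The full-set rule applies only where nothing else is noted, and SAP 5.1 and 5.6.2 each contain another candidate. This stands: it would be wrong to say flatly that the percentages use the whole Safety Set. It does not remove the problem. The by-period tables are required and labelled as Safety Set tables, the base of participants with a TEAE is optional, and none of the candidates is the population at risk in the period.

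**The direction is open.** A reader might infer that pre-pandemic incidence must be understated, or that the tables will show more events during the pandemic even at a constant event rate. The documents do not support either statement. They give no dosing or enrolment dates; if everyone was dosed before the cut-off, the earlier period is not diluted at all. Early completers dilute the later period instead. The optional base can push the percentage up. Main Portion tables contain no Extension time, so which side holds more follow-up there depends on enrolment timing alone.

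**The consequence is small.** The tables are descriptive and shown by arm. With 1:1 randomisation, late enrolment should thin both arms' Main Portion denominators about equally on average, so the between-arm contrast within a period is not systematically distorted. Participant and event counts stand beside each percentage, the listings flag the period, and the demographic tables split by enrolment date let a reader approximate the earlier denominator. All of this stands and limits the weight of the point. The approximation does not help for the later period, because enrolment date does not show whose window had already closed.

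**Rates by preferred term would be too sparse.** With about 24 participants this is right, and the fix does not ask for them.

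**Conclusion.** The point holds as a gap in definition. The by-period TEAE tables and the before/after overview line have no at-risk denominator, and the plan's text offers bases that disagree with one another. On the default base, each period's percentage is scaled by the share of the Safety Set at risk in it. For the earlier period that means a relative understatement anywhere from 0% to 75% over the assumed range of 3 to 12 of 12 per arm; the actual size cannot be read from the documents and may be nil. The boundary gap needs no assumption: an onset on 11 March 2020 is in neither period. The importance is low, because the tables are descriptive and the overall TEAE summaries and overall exposure-adjusted rates are untouched.

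**What to change.** 1. Reconcile the denominator rules in SAP 5.1 with the introductory sentence and the table list in SAP 5.6.2, so that one base governs the by-period tables and the overview line.
2. For each period and arm, make that base the Safety Set participants with at least one day of TEAE time at risk in the period, and display the number.
3. In the combined Main and Extension tables, also show person-time by period. One overall exposure-adjusted rate per period is enough; rates by preferred term are not needed.
4. Define the later period as onsets on or after 11 March 2020.

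The cost is a few lines of SAP text and minor extra programming for descriptive tables. Dosing, visit and onset dates are already collected, so no new data are needed.
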